KABAT TRAINING PROGRAM IN DIAGONAL PATTERN WITH ELASTIC BANDS FOR SHOULDER IN AMATEUR SWIMMERS. A RANDOMIZED CONTROLLED CLINICAL TRIAL

THERA2020

NCT ID NOT YET ASSIGNED

MAY 2023

ABSTRACT

Introduction. The aim of the application of proprioceptive neuromuscular facilitation (PNF) stretching techniques with Theraband® is to improve muscle strength, the range of movement, and the muscular balance of the shoulder in swimmers. The training helps balancing the strength differences between external rotators and internal rotators muscles of the shoulder.

Aim. Analyze the efficacy of the proprioceptive neuromuscular facilitation training with Theraband ®on muscle strength, range of movement and muscular balance of rotator cuff in male swimmers.

Study design. Randomized clinical trial, prospective, single blind.

Methods. All 30 patients will be randomly divided into two groups, experimental and control, through a blinded process with opaque envelopes. The treatment will last 8 weeks with two sessions per week of 4 minutes each. The analyzed variables will be muscle strength (Manual Dynamometer) and the range of motion (goniometer). A descriptive statistical analysis will be performed, calculating the main statistical characteristics. Through the Kolmogorov – Smirnof analysis the normality will be calculated, and through the Pearson correlation test will be calculated the correlation between variables.

Expected results. After the treatment period the intention is to observe an improvement of the external rotator muscles strength of the shoulder as so of the range of motion and muscular balance of the shoulder joint.

Keywords. swimming; Strength; Proprioceptive Neuromuscular Facilitation; Rotator Cuff; Elastic Bands.

1. INTRODUCTION

1.1.INTRODUCTION

In swimming, the upper limbs, and more precisely the rotator cuff, are responsible for adduction and internal rotation movements, allowing the movement of the swimmer's body in the aquatic environment. This overuse of the internal rotators and adductors causes an imbalance of forces in these athletes compared to the external rotators and abductors of the shoulder. Imbalances between these antagonistic muscle groups are responsible for the incidence of rotator cuff injuries or "swimmer's shoulder" (1).

Strength exercises, as well as muscle stretching exercises, have always been integrated into the training of different disciplines to improve the performance of athletes (2). It would therefore be advisable to develop protocols for the prevention of shoulder injuries due to these muscular imbalances, strengthening the muscles responsible for external rotation and abduction of the shoulder (1).

1.2.ETIOLOGY, PREVALENCE AND INCIDENCE

The shoulder is the joint with the greatest degree of movement in the whole body, consequently, the incidence of injuries is very high. In the so-called " overhead athletes ", which include swimmers, among others, injuries to this joint complex have a high prevalence rate (3).

Swimmer's shoulder pain has an incidence rate of 38%. Between 29% and 91% of these athletes have suffered from this symptom throughout their sporting life (4). This data is easily explained since in the water the propulsion forces are based on the impulse through the upper limbs, unlike sports practiced on land where the lower limbs are used preponderantly. The overuse of the shoulder muscles during weekly training sessions,

which can be up to 6 or 7 per week, leads to muscular imbalances between the rotators, which, without preventive treatment, can later lead to injury (3).

1.3.PHYSIOTHERAPY TREATMENT

The most used techniques to increase the strength and muscular balance of the rotator cuff in overhead athletes include scapulohumeral stabilization exercises, plyometrics, maximum strength and electrotherapy application. In recent years, some studies have been published demonstrating the efficacy of resistance exercises with Theraband elastic bands[®] following a diagonal, PNF type pattern of Kabat, mainly analyzing sports that involve biomechanics similar to swimmers', such as handball, volleyball and baseball. Compensatory training with the diagonal Kabat pattern with Theraband [®] has shown positive effects in improving rotator cuff strength. (1, 5, 6, 7, 8, 9, 10).

1.4.THERABAND® TREATMENT

Scientific evidence demonstrates the effectiveness of Kabat diagonal training using the Theraband® following a strength training protocol with progression of external resistance. The elastic bands used ranged from a minimum resistance that corresponded to the yellow color, to the maximum of gold color. In general, the protocols were 6 weeks long, consisting of 3 series of 10 repetitions, 2 times a week. During the execution of the repetitions, the subjective perception of effort (SPE) of each patient was evaluated. When the SPE had a value equal to or less than 6, the repetitions were increased up to a maximum of 25, subsequently increasing the resistance by changing the elastic band. The position of the patients varied according to the studies. In order to avoid compensation of the thorax, the sitting position was the most frequent position chosen. Regarding the fixation point of the elastic band, this varies in 3 points according to the study: head, feet and iliac crest. There is no single consensus in the current literature indicating protocols applied exclusively to swimmers, but most studies focus on overhead type athletes (1, 5, 6, 7, 8, 9).

1.5. JUSTIFICATION OF THE STUDY

The rotator cuff has enormous biomechanical importance in the swimmer's sporting gesture, also leading to a high incidence of injuries (1,4,5). Exercises with Theraband® following a diagonal Kabat pattern to work on strength in all ranges of motion that involve external rotation can have compensatory effects for the overuse of the antagonist musculature, improving joint range of motion. The evidence shown in other overhead sports , with similar biomechanics, supports the idea of benefit in preventing injuries in swimmers. If a beneficial effect is demonstrated in athletes, its inclusion in the training routine of swimmers would be simple, given the ease of application of this technique, the versatility and the short time required to carry out this training at a minimum cost of money (1, 5, 6, 7, 8, 9).

2. HYPOTHESIS

CONCEPT HYPOTHESIS.

- Theraband® training produces significant improvements in external rotator muscle strength, range of motion, scapular displacement, and rotator cuff muscle balance in amateur swimmers.

NULL HYPOTHESIS.

- Theraband® training does not produce statistically significant effects on lateral rotator muscle strength, range of motion, scapular displacement, and rotator cuff muscle balance in recreational swimmers.

ALTERNATIVE HYPOTHESIS.

- Theraband® training produces statistically significant effects on lateral rotator muscle strength, range of motion, scapular displacement, and rotator cuff muscle balance in recreational swimmers.

3. OBJECTIVES OF THE STUDY

MAIN GOAL

- To evaluate the effectiveness of the application of Theraband® techniques on the strength of the external rotator muscles of the rotator cuff of the shoulder in amateur swimmers between 18 and 33 years of age.

SECONDARY OBJECTIVES

- To evaluate the effectiveness of the application of Theraband® techniques on the range of motion of the shoulder in amateur swimmers between 18 and 33 years of age.
- To evaluate the effectiveness of the application of Theraband® techniques on the scapular displacement of the shoulder in amateur swimmers between 18 and 33 years of age.
- To evaluate the effectiveness of the application of Theraband® techniques on the muscular balance of the rotator cuff of the shoulder in amateur swimmers between 18 and 33 years of age.

4. METHODOLOGY

4.1.STUDY DESIGN

randomized controlled clinical trial conducted in amateur swimmers between 18 and 33 years of age, with the objectives of determining if PNF training with the Theraband® is effective on increasing shoulder external rotator strength, range of motion, and muscular balance of the rotator cuff of the shoulder in these subjects.

4.2.SAMPLE RECRUITMENT

Swimmers will be recruited from the following clubs: Royal Spanish Swimming Federation (Madrid) and Universidad Europea de Madrid. After presenting the research project to the directors and managers of the clubs, the athletes of the clubs will be informed verbally and in writing of the objectives and purposes of the study.

Subjects who agree to participate in this clinical trial will be evaluated to determine whether or not they meet the inclusion criteria, they will be given the informed consent form to sign and successively they will be randomized into two groups, the experimental and the control group.

4.3.SELECTION CRITERIA

Subjects with the following characteristics will be included in this study: male swimmers, belonging to an age range between 18 and 33 years; and that they are training at least two days per week.

In the same way, those subjects who present acute infections, those who suffer from shoulder pathologies and those who have not signed the informed consent document will be excluded.

4.4.SAMPLE SIZE JUSTIFICATION

sample size with respect to the samples used in studies carried out prior to this publication with a similar research objective.

4.5.SAMPLE RANDOMIZATION

Study participants who have signed the informed consent and who meet the inclusion criteria will be randomized. Subjects will be randomly assigned to the respective groups through opaque envelopes.

The athletes belonging to the experimental group will carry out PNF training with Theraband®, while those in the control group will not carry out any type of training.

The physiotherapist in charge of carrying out the test measurements (pre and post treatment) will be blinded regarding the assignment of the participants to the two study groups.

4.6.OUTCOME MEASURES

After receiving the informed consent signed by the athletes, the pre-treatment evaluation will be carried out in the aforementioned centers and included in this study. The measurement will be performed by a physiotherapist blinded to the investigation.

After the treatment period, the study participants from both groups (experimental and control) will be assessed again by the same investigator, following the same guidelines as the initial assessment.

In the different study evaluations, 4 variables will be measured: the maximum isometric force of shoulder in external rotation, the range of joint movement, the scapular displacement and the muscular balance between external and internal rotators of the shoulder. The outcome measures used for these variables will be:

Assessment of the maximum isometric strength of the external and internal rotators of the shoulder joint complex. An assessment will be made with the modified sphygmomanometer test validated by Chamorro et al. (2021) (11). It will be used according to the protocol indicated by Souza et al. (2014) (12). Before starting the test, the entire procedure will be explained to the subject, time will be allowed for them to familiarize themselves with the dynamometer and they will have 3 minutes to warm up before starting with 2 test series at minimal effort (13). The unit of measurement of this instrument is the applied force, indicated in Newton (N) (12). The subject will be placed in a supine position on a table, with the trunk held by velcro straps to ensure stability during the test and avoid possible compensation. The subject's upper limb to be evaluated will be placed in a shoulder abduction and 90° elbow flexion, the forearm will be perpendicular to the floor and to the table. The dynamometer will be placed transversely to the distal end of the upper limb, in contact with the patient's wrist, requesting 5-6 series of maximum isometric contractions, for 5 seconds, with 30 seconds of rest between series, respectively in external rotation position and internal. The exerted force will be indicated by the dynamometer and the maximum value reached during each series will be recorded. If the values reached in the 5 contractions exceed a coefficient of variation of 5% or if a pain threshold of 6/10 of the visual analogue scale (VAS) is exceeded, the test must be repeated to guarantee its validity. During the execution of the series, the physiotherapist will maintain firm contact with the dynamometer, applying a resistance parallel to and equal to the force applied by the subject, without allowing the upper limb to move. The patient will be verbally stimulated to make maximum effort during the 5 seconds and the subject will be instructed not to use the Valsalva maneuver during the execution of the test (13).

At the end of the test, the result obtained will be recorded. A higher score indicates a greater application of muscular force (12).

- Joint range of motion in external rotation. The patient will be placed in the supine position on a table with the arm stabilized and a towel placed below the humerus to maintain a position of the arm 10/15° anterior to the coronal plane (in the scapular plane). The patient's arm will be in a 90° shoulder abduction position, the elbow outside the table at 90° flexion, the forearm and wrist in a 0° position (perpendicular to the table and the floor). To carry out the measurement, a goniometer (Tandou_1AA800252®) will be used. The axis will be placed over the central part of the acromion. The fixed arm of the goniometer will be positioned aligned with the vertical perpendicular to the ground, while its mobile arm will be superimposed on the fixed arm, aligned with the longitudinal midline between the ulna and its styloid process (14).
- Rotator cuff muscle balance: with the results of the maximum isometric strength assessment, we will make a ratio between internal and external rotators of each arm (maximum internal rotation isometric force / maximum external rotation isometric force), a value closer to 1 will indicate a better muscular balance (15).
- Scapular displacement: in standing position, the horizontal distance between the inferior angle of the scapula and the corresponding thoracic spinosa is measured in the relaxed position as a baseline measure, and the horizontal displacement of the angle at maximum elevation of the arm is measured using the PALM(16).
- inter-observer reliability analysis will be performed. The principal investigator and the evaluator will evaluate the maximum isometric force of the external rotators of the shoulder and the angle of optimal application of force in a sample of 5 subjects.

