4.7. INTERVENTION

Each session will last approximately 4 minutes per subject, taking place 2 days a week, over a period of 8 weeks. The intervention will be carried out at the beginning of the training session.

Prior to the realization After swimming training, the strength technique with Theraband[®] will be applied to the subjects of the experimental group, asking the control group to follow their usual routine.

The Theraband® intervention will consist of the application of the protocol described by Batahla et al. 2015(1). The objective of the application of the technique is to produce an increase in muscle strength in the external rotators and the optimal angle of force application. The technique will be performed with the patient in a standing position lateral to a wall bar where the elastic band will be fixed at the level of the iliac crest. Each repetition will consist of bringing the end of the elastic band following the diagonal pattern of Kabat D2 for the flexion. It will start from a position of adduction, extension and internal rotation of the shoulder with elbow extension and pronation, flexion and ulnar tilt of the wrist until reaching a position of flexion, abduction and external rotation of the shoulder with elbow extension and supination, extension and radial bend of the wrist. The elastic bands used will have different resistances depending on the color. 2 types of bands will be used respectively from lower to higher resistance. There will be 3 series, of 10 repetitions each, for each upper limb. At the end of each series, the subjective perception of effort of each patient will be evaluated (from 0 to 10), and in the event that it reaches a value equal to or less than 6, 5 repetitions will be added in each series until reaching a maximum. of 20 or SPE greater than 6. When 20 repetitions are reached, the resistance of the Theraband® will be increased by changing the elastic band in the next session, starting again with 10 repetitions (1).

Subjects will be properly instructed in performing the exercises at the start of the protocol by physiotherapists and/or qualified trainers previously trained by the authors.

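### Swim load, which the plan itself treats as a cause of rotator imbalance, is not recorded, and neither stratification nor adjustment is described: a cheap gain in precision and interpretability is missed

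*Combined protocol and SAP*

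**What the plan says.** - **Cause.** Section 1.1 puts the problem down to swimming itself: "This overuse of the internal rotators and adductors causes an imbalance of forces in these athletes". Section 1.2 ties it to the weekly training sessions, "which can be up to 6 or 7 per week, leads to muscular imbalances between the rotators".
- **Outcomes.** Section 3 makes external rotator strength the main goal and rotator cuff balance a secondary one.
- **Eligibility.** Section 4.3 requires of the swimmers "that they are training at least two days per week". That is a floor with no ceiling.
- **Source.** Section 4.2: "Swimmers will be recruited from the following clubs: Royal Spanish Swimming Federation (Madrid) and Universidad Europea de Madrid".
- **Allocation.** Section 4.5: "Subjects will be randomly assigned to the respective groups through opaque envelopes". The abstract adds the total: "All 30 patients will be randomly divided into two groups, experimental and control, through a blinded process with opaque envelopes". No ratio, blocking, stratum or minimisation is described.
- **Data.** Section 4.6 lists four variables: external rotation force, range of motion, scapular displacement, and the balance of internal to external rotators. Swim load is not one of them.
- **Control condition.** Section 4.7 speaks of "asking the control group to follow their usual routine". Section 4.5 says instead that controls do no training of any kind.
- **Blinding.** Section 4.5 blinds the physiotherapist who measures. No blinding of swimmers is described.
- **Analysis.** Section 5 compares groups at baseline with a t-test or Mann–Whitney U test, then fits a 3×2 mixed ANOVA with Bonferroni correction. No covariate is named.

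**The concern.** The plan names a driver of its own outcomes, lets that driver vary freely between participants, and then does not collect it. Three things follow.

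First, if load affects the 8-week change in strength or balance, its variance stays in the error term, and a small trial can ill afford that. Second, with so few swimmers the arms may by chance differ in load. The planned baseline comparison cannot show this, because it covers only what is collected. Third, swimmers will know whether they do band work. If either group swims more or less as a result, that difference arises after randomisation, is not covered by chance-based error rates, and leaves no trace in the data. The two descriptions of the control condition make this worse: read literally, the one in 4.5 would make load differ between arms by design.

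**Working it through.** **The plan's own figure.** The total is 30. Section 4.4 justifies it only by "sample size with respect to the samples used in studies carried out prior to this publication with a similar research objective", with no alpha, power, effect size, SD or dropout, so it cannot be reproduced. Working backwards, with 15 per arm, two-sided alpha 0.05 and 80% power (all assumed), the detectable difference is (1.960 + 0.842) × √(2/15) = 1.02 SD, or 1.06 SD with the t distribution. Only large effects are within reach, so precision matters.

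**Chance difference in load.** The standard error of the difference in mean load, in SD units of load, is √(1/15 + 1/15) = √(2/15) = 0.365. Then

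P(|difference| ≥ 0.5 SD) = 2 × [1 − Φ(0.5/0.365)] = 0.171, about 17%.

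A simulation of 200,000 allocations, with load spread evenly over 2 to 7 sessions a week (SD 1.71, so 0.5 SD is 0.85 sessions), gives 18%. A difference of at least one session a week occurs in 12%. The range 2 to 7 is an assumption: the documents give the lower end as a criterion and 6 or 7 only as background on swimmers.

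**Effect on the contrast.** If load correlates r with 8-week change, a 0.5 SD load difference shifts the group contrast by 0.5 × r SD. The documents give no r, so a range is shown. The same simulation, with no true effect, gives:

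| r | Shift at 0.5 SD | Type I error, all allocations | Load differs ≥ 0.5 SD | Otherwise |
|---|---|---|---|---|
| 0.3 | 0.15 SD | 5.0% | 7.3% | 4.5% |
| 0.5 | 0.25 SD | 5.0% | 11.6% | 3.6% |
| 0.7 | 0.35 SD | 5.0% | 17.8% | 2.2% |

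The middle column matters most: over all allocations the error rate is nominal. The next column shows what an unlucky allocation would do unseen.

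**With load recorded and adjusted for.** ANCOVA on load gives type I error of 5.0% overall and 4.8% to 5.0% when load differs by 0.5 SD or more. Power at a true difference of 1.0 SD rises from about 75% to 78%, 85% or 95% for r = 0.3, 0.5 or 0.7.

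**Club as a proxy.** Assume 15 swimmers per club and 15 per arm. The hypergeometric probability that a club splits 10:5 or worse is 0.143. At 10:5, a club difference of d in 8-week change shifts the contrast by (10/15 − 5/15) × d = d/3, that is 0.17 SD at d = 0.5 and 0.33 SD at d = 1. Adjusting for club removes (d²/4)/(1 + d²/4) of the variance: 5.9% at d = 0.5 and 20% at d = 1. The standard error then shrinks by 1 − √0.941 = 3% or 1 − √0.80 = 11%. Both values of d are assumptions.

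**The case against.** The strongest reply is that chance imbalance in an unmeasured factor is ordinary sampling error, present in every trial of 30 and already covered by the test. That stands. The overall type I error is 5%, and every shift computed above is smaller than one standard error of the contrast (0.365 SD). A reader might infer that the design biases the result towards a band effect; the documents and the figures do not support that.

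Measuring before and after also removes stable strength differences left by past training. Only the effect of load on change over the 8 weeks remains, and the documents do not quantify it. That stands too.

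Other inferences are tempting but go beyond the text:
- That load varies over the season and the arms start at different times. The documents give no calendar, recruitment window or season phase. If the arms are randomised concurrently, season affects both equally in expectation.
- That all envelopes form one unblocked stack. Section 4.5 is silent on this; it does not say so.
- That one club trains harder. Section 4.2 names two sources and says nothing of their programmes.

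Club is only a proxy, so adjusting for club alone would leave load differences within a club untouched. Very small blocks within each club could also make the next allocation guessable.

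What the reply does not answer is that load, the plan's own causal factor, goes unrecorded, so precision is given away and a change in swimming behaviour by unblinded participants cannot be seen.

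**Conclusion.** The point holds as a minor one with a cheap remedy. The plan treats swim load as a cause of the imbalance it studies, sets only a lower limit on it and recruits from two clubs. It does not list load as data, describes no stratification and names no covariate.

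The validity of the test over all allocations is not in question. The cost is a power gain forgone (3, 10 or 20 percentage points at a 1.0 SD effect, for r = 0.3, 0.5 or 0.7), a roughly one-in-six chance of a load difference of 0.5 SD or more that nobody could detect or correct, and no evidence on swimming during the trial. These sizes rest on 15 per arm and the assumed correlations; the power figures also assume load spread evenly over 2 to 7 sessions. If load has little bearing on 8-week change, the precision gain is small, but the log would still show what each group did.

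**What to change.** 1. **Record baseline load.** Enter usual weekly swim sessions as a number in 4.6. Training frequency must already be asked to apply the criterion in 4.3.
2. **Prespecify the adjustment.** In section 5, name baseline sessions and club as covariates in the main between-group analysis of change. In a mixed ANOVA they must act on the change over time: a covariate entered only as a between-subject main effect leaves the group-by-time contrast unadjusted.
3. **Log load during the trial.** Record weekly swim sessions in both groups over the 8 weeks and report them by group, descriptively. Do not adjust for them, because they arise after randomisation and may be affected by allocation.
4. **Allocate within club.** In 4.5, prepare a separate sequence of opaque envelopes per club, with varying block sizes concealed from those who enrol. Avoid blocks so small that the next allocation can be guessed.
5. **Reconcile the control condition.** Sections 4.5 and 4.7 describe it differently and must be made to agree.

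The cost is a short attendance log, two envelope sequences instead of one, and two model degrees of freedom (from 30 − 2 = 28 to 26). No extra swimmers or strength tests are needed. Someone must be assigned to keep the log, since the documents do not say who would.

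### The strength-test procedure requires a repeat of the maximal test when pain exceeds 6/10, with no stated delay and no pain stop in the text provided: a minor participant-safety defect in the wording.

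*Combined protocol and SAP*

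**What the plan says.** The isometric strength test is described in section 4.6 (Outcome measures). Each test consists of "requesting 5-6 series of maximum isometric contractions, for 5 seconds, with 30 seconds of rest between series", in external and in internal rotation. Effort is meant to be maximal: "The patient will be verbally stimulated to make maximum effort during the 5 seconds". The assessor resists the movement by hand: "the physiotherapist will maintain firm contact with the dynamometer", matching the force that the swimmer applies.

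The repeat rule has two triggers. The first is inconsistent readings: "If the values reached in the 5 contractions exceed a coefficient of variation of 5" per cent. The second is pain, and the consequence is the same for both: "if a pain threshold of 6/10 of the visual analogue scale (VAS) is exceeded, the test must be repeated to guarantee its validity".

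Three other statements bear on the point:

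- Section 4.3 excludes at entry "those who suffer from shoulder pathologies".
- Section 4.6 has the post-treatment assessment done "following the same guidelines as the initial assessment", so the repeat rule applies at both visits.
- For the sphygmomanometer test, section 4.6 also defers to a published method (reference 12): "It will be used according to the protocol indicated by" that source.

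**The concern.** The two triggers are different in kind. A coefficient of variation above 5% suggests uneven effort or technique, and measuring again is a sensible answer. Pain above 6/10 during a maximal contraction is a reason to stop loading that shoulder. The protocol treats the two alike and makes the repeat mandatory.

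What is at stake is participant safety. An assessor who follows the sentence literally could ask a swimmer who has just reported pain above the threshold for another full set of verbally encouraged maximal contractions with the same arm. If the pain returned, the same sentence would apply again, and no limit on repeats is stated.

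**Working it through.** The plan gives no figure to reproduce here. The check has three parts: what the text says about pain during testing, the load that one repeat adds, and what a stop rule would cost.

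**1. Text check**

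| Question | What the supplied text says |
|---|---|
| Is the repeat optional? | No; section 4.6 makes it mandatory |
| When is it done? | Not stated; the only interval given is the 30 s between series |
| Is there a limit on repeats? | None stated |
| Is there a pain stop in the test procedure? | None |
| Is there a withdrawal or adverse-event rule elsewhere? | None |
| Related protections | Shoulder pathology excluded at entry (4.3); 3-minute warm-up and two minimal-effort series before the test (4.6); testing by a physiotherapist (4.5, 4.6) |

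The protections lower the chance of pain above 6/10. None of them says what to do once it occurs. The entry exclusion is applied before randomisation, so it does not reach pain provoked by the test itself or a shoulder that has become painful by the second assessment, 8 weeks of training later.

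**2. Load added by one repeat**

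Inputs, all from section 4.6: 5 or 6 contractions, 5 s each, 30 s rest between them.

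- Maximal effort, one direction: 5 × 5 = 25 s, or 6 × 5 = 30 s.
- Elapsed time, one direction: 5 × 5 + 4 × 30 = 145 s, or 6 × 5 + 5 × 30 = 180 s.
- If the repeated test means both directions of that arm: 2 × 5 = 10 to 2 × 6 = 12 contractions, and 50 to 60 s of effort.

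One repeat therefore doubles the load on the arm, from 5–6 to 10–12 contractions in one direction, or from 10–12 to 20–24 over both.

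**3. Cost of a stop rule in precision**

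Assumptions: the 30 participants named in the Abstract split 15 and 15; a two-sample t-test on strength at two-sided 5% with 80% power (the plan states neither level); and, as a pessimistic case, a swimmer stopped for pain counted as wholly lost.

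The detectable standardised difference d solves

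P(|T| > t₀.₉₇₅,ν) = 0.80, where T is noncentral t with ν = n₁ + n₂ − 2 degrees of freedom and noncentrality d × √(n₁n₂/(n₁ + n₂)).

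| Analysed | ν | Critical t | √(n₁n₂/(n₁+n₂)) | d (SD) |
|---|---|---|---|---|
| 15 v 15 | 28 | 2.048 | 2.739 | 1.06 |
| 15 v 14 | 27 | 2.052 | 2.691 | 1.08 |
| 14 v 14 | 26 | 2.056 | 2.646 | 1.10 |

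Losing one swimmer per arm raises the detectable difference by 1.10 − 1.06 = 0.04 SD, about 4%.

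No event rate is worked out. The documents give no rate of pain above 6/10 during testing, and any assumed rate would only return the assumption.

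**The case against.** The strongest reply is that the sentence is a rule about which readings to accept. Its stated purpose is validity, so the authors may have meant only that a painful attempt does not count and should be redone once the pain has settled. That reading is open, because no timing is given. It stands as far as this: the text does not order an immediate repeat. It does not remove the point, because the text does not require a delay either, and a rule about pain should not leave that to interpretation.

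A reader might go further and infer that the repeat defeats its own purpose because any value obtained after pain is untrustworthy. The documents do not support that. The rule already treats the painful attempt as not valid, it would apply again to the repeat, and a retest after recovery could give a sound maximum.

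A reader might also infer bias between the arms. Nothing shows it: the rule is the same in both groups and the assessor is blinded to allocation (section 4.5).

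Other mitigating facts are real. The assessor matches the swimmer's force and does not overpower the arm, so the swimmer can ease off. The warm-up and minimal-effort series give pain a chance to show early. Participants are 18 to 33 years old and free of shoulder pathology at entry. Reference 12, to which the method defers, may contain a pain rule, and the consent pages, which are not in the supplied text, may state a general right to stop. These make harm less likely. They do not correct a written instruction that says the opposite of stopping.

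**Conclusion.** The point holds as a minor participant-safety defect in one sentence. The protocol's mandatory response to pain above 6/10 is another maximal test; its wording permits that test to follow at once, and no pain stop appears in the text provided. The added load, if a repeat is done, is 25 to 30 s of maximal effort in one direction, or 50 to 60 s over both directions of the arm.

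The frequency is unknown, and nothing in the documents shows that the rule would injure anyone or distort the comparison. The conclusion rests on the supplied text alone; a stop rule in the consent form or in reference 12 would soften it but would still conflict with section 4.6 as written. It is best treated as a cheap improvement.

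**What to change.** Separate the two triggers in section 4.6:

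- **Coefficient of variation above 5%:** repeat the test, as now.
- **Pain above 6/10:** stop testing that arm for the session, record the event, do not use that value as a valid maximum, and retest only after recovery at the physiotherapist's discretion.

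The cost is one sentence of procedure and one data field for a pain stop. The downside is possibly a few missing strength values, with the small loss of precision shown in the working.
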